### 7.3 Follow-up and Final Visits

#### Follow-up visits: Days 7, 14, 28, 90, 180.

- Study participants will be asked to return for five follow up visits, with the respective window periods, per the table below:

Day	7	14	28	90	180
Time point					
Window	+/- 1	+/- 2	+/- 3	+/- 10	+/- 14 (a 90 day window expansion is being requested)
Blood Volume	96mL	96mL	64mL	64mL	64mL

- Medical history will be reviewed and updated as appropriate.
- All concomitant medications taken since the previous study visit will be recorded on the appropriate data collection form. Previously recorded medications will be updated as appropriate.
- Study personnel will discuss with participants and assess and record all AE/SAEs. Previously recorded AE/SAEs will be updated as appropriate.
- Approximately the amount of venous blood, as indicated by the table above, will be collected for research assays.
- Targeted physical exam will be done only as dictated by a change in medical history.
- A urine pregnancy test will be performed on all female participants of childbearing potential

for any visit longer than 14 days from the last pregnancy test..

- Follow-up visits were also halted, which impacted several participants' Day 180 follow-up visit.
- We are requesting that the windows for the Day 180 visit be extended by 90 days.
- Extending the window for the Day 180 follow-up visits would allow samples from participants whose visits were halted at this time point to be collected once the Emory restrictions regarding COVID-19 are lifted and staff can reasonably collect samples, dependent upon when the University and applicable Unit and School allow. The scientists feel that the samples, even if a few months late, will greatly help evaluate the longevity of the responses to flu vaccines.
- Study activities will not be changed, just the timing of the Day 180 visit.

#### **7.4 Early Termination Visit**

There are no special or routine evaluations to be done at an early termination visit; subjects will not be asked to come in for an additional visit if they decide to end their participation in the study or the study is terminated. If the study is terminated early, the subject will be informed via telephone of the reason for early termination.

#### **7.5 Unscheduled Visit**

Unscheduled visits are not anticipated with this study, but may occur at any time during the study. Any of the following activities may be performed:

- Medical history will be reviewed and updated as appropriate.
- All concomitant medications taken since the study visit will be recorded on the appropriate data collection form. Previously recorded medications will be updated as appropriate.
- Study personnel will discuss with participants and assess and record all AE/SAEs. Previously recorded AE/SAEs will be updated as appropriate.
- Vital signs, including oral or axillary temperature, pulse, blood pressure and will be obtained.
- A targeted physical examination will be performed by a study clinician licensed to make medical diagnoses and listed on the Form FDA 1572 as the site principal investigator or sub-investigator.

- Approximately 10 mL of venous blood will be collected for chemistry and/or hematology performed by the local or site laboratory if deemed necessary by [name] or a designee.
- A urine pregnancy test will be performed on all female participants of childbearing potential.

## 8 STUDY PROCEDURES AND EVALUATIONS

### 8.1 Clinical Evaluations

- Clinical interview of subject at screening to include:
  - Demographics: age, date of birth, gender, ethnicity, race
  - History of allergies: food, drug, environmental, specifically solicit if any allergy to vaccines or eggs
  - History of influenza vaccination, and previous reactions, if any
  - History of Guillain-Barre syndrome
  - History of medications taken within the past 90 days to include prescription and over the counter medications, specifically solicit if any blood thinners or immunosuppressive agents have been used
  - History of any vaccinations within the past year
  - Acute or chronic medical conditions as reported by subject
- Vital signs (blood pressure, pulse, temperature, height, weight)
- Targeted physical exam
- Collection of blood for clinical laboratory tests at screening visit (16 ml)
- Collection of research blood samples at study visits: day 0 (48 ml), 7, 14 (96 ml), 28, 90 and 180 (64 ml).
- Administration of licensed seasonal inactivated influenza vaccine by the clinical research nurse at Day 0
- Clinical health assessment at follow up study visit to include inquiry regarding any illness, any change in medication, and any overall health changes since last study visit.
- A urine pregnancy test will be performed on all female participants of childbearing potential and must be negative.

### 8.2 Laboratory Evaluations/Assays

The participating laboratories are Emory Medical Laboratories.

The following clinical laboratory evaluations will be performed in the study:

- Urine Pregnancy Test for women of childbearing potential

- Hematology: hemoglobin, white blood cells (WBC), platelet count. [Acceptable ranges: WBC: Male- 4.2-9.1/uL, Female- 4-10/uL; Hemoglobin: Male- 12.9-16.1/dL, Female- 11.4-14.4/dL; Platelet 150-400/uL]
- Chemistries: creatinine, liver enzymes [Acceptable ranges: calculated Glomerular filtration rate (GFR)  $\geq$  60 mL/min/1.73 m^2; Albumin  $\geq$  3.5 gm/DL; ALT  $<$  66 u/L; AST  $<$  62 u/L]

#### Research Laboratory Assays:

- Innate responses in the blood and mucosal sites: The serum analyses of cytokines and chemokines associated with innate immunity will be determined by multiplex analysis,, including IP-10, Th1 cytokines (IFN- $\gamma$ , TNF, IL-2), Th2 (IL-4, IL-5, IL-13) and regulatory (IL-10) cytokines. Flow cytometric analysis of innate cell populations (dendritic cell subsets, monocyte subsets, NK cell subsets and innate lymphoid cells) will be performed using antibody panels routinely in use in the research laboratory
- B cell and CD4 T cell responses: The following influenza virus-specific responses will be analyzed in the blood after vaccination:
  - Serum antibody: We will measure the HAI titers, neutralizing antibody responses, and the influenza-specific serum antibody levels (IgG, IgA, and IgM) using ELISA at all time-points.
  - Plasmablasts: The influenza-specific plasmablast response will be quantitated using both ELISPOT and flow cytometry at day 7 post-vaccination.
  - Memory B cells: The kinetics of the IgG memory B cell influenza-specific response will be quantitated using an established assay.
  - CD4 T cells: The HA-specific CD4 T cell responses will be quantitated at each time point by ex vivo stimulation using overlapping HA peptides or HA protein of the different influenza strains present in the vaccine. The following cytokines will be analyzed using ICS or ELISPOT: Th1 cytokines (IFNg, TNF- $\alpha$ , and IL-2); Th2 cytokines (IL-4 and IL-10); and TFH cytokines (IL-21 and IL-4). We will put a specific focus on analyzing CD4 T follicular helper (TFH) responses since these cells specialize in B cell help and are critical for the formation and maintenance of germinal centers. The germinal center reaction, in turn, is necessary for the generation of high affinity antibody responses and memory B cells. In addition, TFH cells secrete the cytokine IL-21 that is essential for generating long-lived plasma cells and sustaining antibody responses. Therefore the generation of long-term humoral immunity is critically dependent on CD4 TFH cells.

#### **8.2.1 Specimen Collection, Preparation, Handling and Shipping**

Samples will be drawn, labeled and logged by a skilled clinical research nurse or phlebotomist, under the supervision of the principal investigator and in accordance with site specific SOPs. Checklists will be utilized to verify appropriate sample collection, transportation, processing, and storage.

Subjects consented to participate in this study will also be asked to consent to storage of any unused blood for future assays. If new studies are identified, the de-identified samples of subjects who have consented to storage of their unused blood will be utilized.

### **8.3 Procedures to be followed in the Event of Abnormal Laboratory Test Values or Abnormal Clinical Findings**

For subjects with values in the clinically significant range, the lab abnormalities will be explained to the study participant by the principal investigator or a designee. The designee may be clinical study personnel (Clinical Research Coordinator, Study Coordinator or Research Nurse) as indicated on the Delegation of Authority log. The subject will be given a copy of his or her abnormal lab report and instructed to follow up with his or her primary health care provider or health clinic. Abnormal clinical values obtained from screening labs, which are done prior to treatment, will be considered to render the subject a screen failure and will not be considered to be adverse events. Any subject with Lab values outside of clinical range will be informed of the value and referred to their PCP for follow up.

## 9 ASSESSMENT OF SAFETY

### 9.1 Specification of Safety Parameters

Only FDA approved, licensed seasonal inactivated influenza vaccine will be administered in this protocol as standard of care during influenza vaccine season, following the manufacturers' instructions and safety precautions.

For the purposes of this study, reportable adverse events are limited to any occurrence or worsening of an undesirable or unintended sign, symptom or disease that is specifically associated with a study procedure that is not part of the normal standard of care for the participant. As previously mentioned, there are minimal risks associated with venipuncture for obtaining research related labs. Foreseeable adverse events associated with venipuncture are: mild, temporary discomfort at the venipuncture site, bruising, and phlebitis. Very rarely, subjects may experience "vaso-vagal syndrome" during phlebotomy. Vaso-vagal reactions may include diaphoresis, nausea, syncope and rarely loss of consciousness.

Anticipated adverse events related to administration of the inactivated influenza vaccine include: localized erythema, induration, swelling, itching and/or pain at the injection site, mild fever, myalgia, headache and malaise following vaccination. Since immunization with flu vaccine annually is offered as standard of care to healthy adults to prevent influenza infection, these anticipated reactions to the vaccine will not be considered reportable adverse events. Illness requiring hospitalization as deemed related to vaccination will be reported as an adverse event.

Any adverse event listed by the vaccine manufacturer as a contraindication to further doses of the vaccine will be considered an adverse event for the study.

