#### **Adverse Event:**

ICH E6 defines an AE as any untoward medical occurrence in a subject or clinical investigation participant administered a pharmaceutical product regardless of its causal relationship to the study treatment. An AE can therefore be any unfavorable and unintended sign (including an abnormal laboratory finding), symptom, or disease temporally associated with the use of medicinal product. The occurrence of an AE may come to the attention of study personnel during study visits and interviews of a study recipient presenting for medical care, or upon review by a study monitor.

All AEs including local and systemic reactions not meeting the criteria for "serious adverse events" will be captured on the appropriate CRF. Information to be collected includes event description, time of onset, clinician's assessment of severity, relationship to study product (assessed only by those with the training and authority to make a diagnosis, which would include MD, PA, Nurse Practitioner, DO, or DDS), and time of resolution/stabilization of the event. All AEs occurring while on study will be documented appropriately regardless of relationship. All AEs will be followed to stabilization or resolution.

Any medical condition that is present at the time that the subject is screened will be considered as baseline and not reported as an AE. However, if it deteriorates at any time during the study, it will be recorded as an AE.

All AEs will be graded for severity and relationship to study product.

FDA defines an AE as any untoward medical occurrence associated with the use of a drug in humans, whether or not considered drug related.

**Severity of Event:** All AEs will be assessed by the clinician using a protocol defined grading system. For events not included in the protocol defined grading system, than the following guidelines will be used to quantify intensity.

- Mild: events require minimal or no treatment and do not interfere with the subject's daily activities.
- Moderate: events result in a low level of inconvenience or concern with the therapeutic measures. Moderate events may cause some interference with functioning.
- Severe: events interrupt a subject's usual daily activity and may require systemic drug therapy or other treatment. Severe events are usually incapacitating.

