- Life threatening: any adverse drug experience that places the subject or subject, in the view of the investigator, at immediate risk of death from the reaction as it occurred, i.e., it does not include a reaction that had it occurred in a more severe form, might have caused death.

Changes in the severity of an AE will be documented to allow an assessment of the duration of the event at each level of intensity to be performed. Adverse events characterized as intermittent will require documentation of onset and duration of each episode.

**Relationship to Study Products:** The clinician will assess an AE's relationship to influenza vaccine as part of the documentation process, but it is not a factor in determining what is or is not reported. All AEs will have their relationship to study product assessed using the terms: related or not related using the following guidelines:

- Related – There is a reasonable possibility that the study product caused the adverse event. Reasonable possibility means that there is evidence to suggest a causal relationship between the study product and the adverse event.
- Not Related – There is not a reasonable possibility that the study product caused the event.

Adverse events will be followed until resolved or considered stable. Any adverse event listed by the vaccine manufacturer as a contraindication to further doses of the vaccine will be considered an adverse event for the study. Any adverse event listed in the VAERS Table of Reportable Events Following Vaccination found using the following link [http://vaers.hhs.gov/resources/VAERS\\_Table\\_of\\_Reportable\\_Events\\_Following\\_Vaccination.pdf](http://vaers.hhs.gov/resources/VAERS_Table_of_Reportable_Events_Following_Vaccination.pdf) that occurs within the specified time period after vaccination or, if in the judgment of the PI, any unexpected reaction to the vaccine will be reported to VAERS with a copy faxed or emailed to the DMID CPM and MO at time of VAERS reporting. These reports will be made using the timelines outlined at [https://vaers.hhs.gov/resources/VAERS\\_Table\\_of\\_Reportable\\_Events\\_Following\\_Vaccination.pdf](https://vaers.hhs.gov/resources/VAERS_Table_of_Reportable_Events_Following_Vaccination.pdf).

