#### 9.2.2 Serious Adverse Events

**Serious Adverse Event (SAE):** Serious Adverse Events will be collected from the time the participant begins the study until study completion, or until the participant withdraws from the study. SAE's will be documented on the Adverse Event form and reported to the DMID CPM and MO.

- All deaths and life-threatening events, regardless of relationship will be recorded on the SAE form and sent by fax to DMID CPM and MO within 24 hours of site awareness of the death or life-threatening event.
- All other SAEs, regardless of relationship will be recorded on the SAE form and sent by fax within 72 hours of becoming aware of the event.

A Serious Adverse Event is defined as an AE meeting one of the following conditions:

- Death during the period of protocol defined surveillance
- Life Threatening Event (defined as a subject at immediate risk of death at the time of the event)

- An event requiring inpatient hospitalization or prolongation of existing hospitalization during the period of protocol defined surveillance
- Results in congenital anomaly or birth defect
- Results in a persistent or significant disability/incapacity.
- Any other important medical event that may not result in death, be life threatening, or require hospitalization, may be considered a serious adverse experience when, based upon appropriate medical judgment, the event may jeopardize the subject and may require medical or surgical intervention to prevent one of the outcomes listed above. Examples of such medical events include allergic bronchospasm requiring intensive treatment in an emergency room or at home, blood dyscrasias or convulsions that do not result in inpatient hospitalization, or the development of drug dependency or drug abuse.

Events **not** considered to be serious adverse events are hospitalizations for the:

- routine treatment or monitoring of the studied indication not associated with any deterioration in condition.
- treatment, which was elective or pre-planned, for a pre-existing condition that is unrelated to the indication under study and did not worsen
- treatment on an emergency, outpatient basis for an event **not** fulfilling any of the definitions of serious given above and **not** resulting in hospital admission

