### **9.3 Reporting Procedures and Safety Oversight**

This is a minimal risk study. Due to its nature very few, if any, serious adverse events are likely to be chronologically or causally related to study procedures, and any adverse events that do occur are likely to be mild, transient, and self-limiting. Therefore, adverse events, including serious adverse events, will be collected and reported to the IRB/IEC and DMID except for anticipated reactions noted in Section 9.2.1, an Independent Safety Monitor will not be required, and a formal Safety Monitoring Committee will not be constituted. All Adverse events will be communicated to the DMID and to the IRB as delineated by Emory Internal Review Board reporting requirements stated in section 9.2.1 and 9.2.2.

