## **9.6 Safety Oversight**

Serious and severe adverse events will be reported to DMID. DMID has the authority to stop study enrollment, vaccinations and procedures if AEs are reported that meet halting criteria.

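### Sections 9.1 and 9.3 exempt anticipated vaccine reactions that 9.2.1, 9.6 and 9.3's own last sentence require to be recorded or reported, so it is unclear whether and when severe non-serious reactions reach DMID

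*Combined protocol and SAP*

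**What the plan says.** **Section 9.1** limits reportable adverse events to those "specifically associated with a study procedure that is not part of the normal standard of care for the participant". It lists the anticipated vaccine reactions (redness, induration, swelling, itching or pain at the site, mild fever, myalgia, headache, malaise) and, because annual vaccination is standard of care, states that "these anticipated reactions to the vaccine will not be considered reportable adverse events". It then adds: "Illness requiring hospitalization as deemed related to vaccination will be reported as an adverse event".

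**Section 9.2.1** requires non-serious events, local and systemic reactions among them, to be captured on the CRF: "All AEs occurring while on study will be documented appropriately regardless of relationship". Of the assessed relationship to vaccine it says "it is not a factor in determining what is or is not reported". Events below the IRB reporting threshold go to the clinical project manager in monthly reports and to the IRB at annual review. VAERS-listed or unexpected vaccine reactions go to VAERS, with a copy to the DMID project manager and medical officer.

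**Section 9.2.2** sends deaths and life-threatening events to DMID within 24 hours. For the rest: "All other SAEs, regardless of relationship will be recorded on the SAE form and sent by fax within 72 hours".

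**Section 9.3** has adverse events collected and reported to the IRB and DMID "except for anticipated reactions noted in Section 9.2.1". Its last sentence has all adverse events communicated to both bodies, along the lines of 9.2.1 and 9.2.2.

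**Section 9.5** has three halting criteria. The first (laryngospasm, bronchospasm or anaphylaxis) and the third (the same or a similar severe or life-threatening event in two or more participants) refer to association with a study procedure. The second (any associated SAE) refers to study product or procedure.

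**Section 9.6** states: "Serious and severe adverse events will be reported to DMID". It gives DMID authority to stop the study if reported events meet the halting criteria.

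**The concern.** These are operative instructions to site staff, and no section is given precedence. A nurse who hears at Day 7 of severe myalgia after vaccination finds one section that says to record it, one that says not to collect it, one that says it is not reportable, and one that says it goes to DMID.

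Sections 9.3 and 9.7 provide for no independent safety monitor and no safety monitoring committee. DMID's stopping authority under 9.6 is tied to events that have been reported to it, so the reporting rule determines what DMID can act on. The content of the safety data listed in 15.3 also depends on which instruction is followed.

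**Working it through.** The plan states no figure on this point, so the check is a side-by-side reading by type of event.

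| Event | Text that leaves it out | Text that brings it in |
|---|---|---|
| Anticipated reaction, not severe, not serious | 9.1 (not reportable); 9.3 (neither collected nor reported) | 9.2.1 (CRF, monthly report); 9.3 last sentence |
| Anticipated reaction, severe but not serious | The same; only fever has a severity limit in 9.1 | The same, plus 9.6 (to DMID, no deadline) |
| SAE unrelated to any study procedure | 9.1, through its limit on what is reportable | 9.2.2 (24 or 72 hours, any relationship); 9.6 |
| Bronchospasm or laryngospasm after vaccination, neither serious nor severe | 9.1, since it calls vaccination standard of care | 9.2.1 (VAERS copy if listed or unexpected, otherwise monthly report) |

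**Recording.** Section 9.1 restricts only what is reportable, so it does not itself bar recording. Section 9.3 does, because its exception covers collection. That conflicts directly with the CRF rule in 9.2.1.

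**Reporting.** Sections 9.1 and 9.3 exempt by type of reaction. Section 9.2.1 contains no such exemption, and neither does 9.6. Section 9.3 also contradicts itself, since its last sentence covers all events.

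**Serious events.** The limit in 9.1 would leave out an SAE unrelated to a study procedure, and 9.2.2 includes it.

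**Cross-reference.** Section 9.3 cites 9.2.1 for the anticipated reactions. The list is in 9.1.

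**Tracing the halting criteria to DMID.**

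- Second criterion (associated SAE): a timed route in 9.2.2, repeated without a time in 9.6.
- First criterion: its events are not on the anticipated list. They reach DMID through 9.2.2 if serious, 9.6 if severe, the VAERS copy if listed or unexpected, and otherwise the monthly report.
- Third criterion: life-threatening events go through 9.2.2. Severe, non-serious events rely on 9.6, without a deadline, or on the monthly report. For anticipated reactions, 9.1 and 9.3 contradict both routes.

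Whether a severe vaccine reaction counts under the third criterion depends on whether vaccination is a study procedure. The second criterion names product and procedure separately, which suggests a distinction; the document does not settle it.

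**Illustration under assumed rates.** The documents give no rate of severe reactions. Let p be the assumed chance that one enrolment has a given severe reaction, and n the number of enrolments. The chance of two or more is 1 − (1 − p)^n − n·p·(1 − p)^(n−1). For n = 70 (the enrolment ceiling) and p = 1%: 1 − 0.4948 − 0.3499 = 15.5% after rounding.

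| p (assumed) | 0.5% | 1% | 2% | 3% | 5% |
|---|---|---|---|---|---|
| n = 70 | 4.8% | 15.5% | 41.0% | 62.5% | 87.1% |
| n = 50 (Section 11.2) | 2.6% | 8.9% | 26.4% | 44.5% | 72.1% |

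This treats enrolments as independent, although re-enrolled subjects are counted again, and it bears on the third criterion only if vaccination is a study procedure. It shows that a count of two is neither negligible nor certain over the assumed range. It does not estimate what will happen.

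**The case against.** The strongest reply is that every event counted in 9.5 has at least one written route to DMID: 9.2.2 for serious events, 9.6 for severe ones, the VAERS copy and the monthly report for others, and the last sentence of 9.3 for all. That stands. A reader might infer that halting events may never reach DMID, and the documents do not support it. Non-arrival would require staff to follow the narrow text of 9.1 and 9.3 over all of these. Uncertainty about whether and when is what the text supports.

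A second reply is that reactions are simply captured but not reported. This fails: the exception in 9.3 covers collection too, and 9.6 and the monthly report still conflict with 9.1 on reporting.

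Four other stronger readings should also be set aside.

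- *That DMID is the only check.* Section 9.5 says the study will be halted and does not make this depend on DMID. The investigator or designee reviews severity and causality (Section 13), source documents are reviewed weekly (10.1, 13), the IRB receives events (9.2.1), and the institution or the FDA may stop the study (5.3).
- *That the hospitalisation sentence in 9.1 contradicts 9.2.2.* It does not say that only vaccine-related hospitalisation counts, and 9.2.2 defines an SAE as a kind of adverse event. The conflict lies in the limiting sentence of 9.1.
- *That the 10-64% soreness rate in 2.3.1 measures the problem.* It describes soreness lasting under two days, among effects called generally mild. It gives no rate of severe reactions.
- *That safety data could not be pooled across seasons.* There is one site, Section 11 plans no safety analysis, and nothing indicates that staff would switch rules between seasons.

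**Conclusion.** The contradiction is in the current text and does not depend on any assumption. Recording of anticipated reactions conflicts between 9.2.1 and 9.3. Their reporting conflicts between 9.1 and 9.3 on one side and 9.2.1, 9.6 and the last sentence of 9.3 on the other. The limit in 9.1 conflicts with 9.2.2 for SAEs, and 9.3 carries a wrong cross-reference.

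The practical consequence is narrow. Serious and life-threatening events have a clear 24/72-hour route in 9.2.2. What is left open is whether, and by when, severe non-serious vaccine reactions reach DMID, and whether they count towards the third halting criterion. How many participants this concerns cannot be derived from the documents. No primary or secondary outcome in Section 3.2 is affected. It is worth correcting because the rules govern safety reporting, cannot all be followed, and are cheap to reconcile.

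**What to change.** - Reconcile 9.1, 9.2.1, 9.2.2, 9.3 and 9.6 into one statement, preferably a table, of what is recorded on the CRF, what goes to DMID and when, and what goes to the IRB and when. State whether severity changes the handling of anticipated reactions, and give a time for severe non-serious events.
- Correct the cross-reference in 9.3.
- Reconcile the wording of the three criteria in 9.5, so that it is clear whether vaccination falls under the first and third.
- Check that every event type counted in 9.5 is on the list sent to DMID under 9.6.

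What is reportable, and what should count towards halting, is for the sponsor and the IRB to decide; the passages need only agree. The cost is protocol wording and possibly a few more lines in the monthly report.
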